An initial pilot safety study will assess the risk of an infant overheating and/or experiencing lowered respiration via measurement of vital signs in a controlled clinical environment while wearing a weighted wearable blanket. Participants will also be observed for any hindrance in their ability to move due to the weighted wearable blanket. A member of the study team will be present during the intervention and continuously monitor the infant's vital signs, allowing for immediate evaluation and correction if needed. We plan to expand this study to include an at-home cohort in the near future (see secondary objective).

Objectives

- Primary Objective:**
 To pilot an investigation on the impact of weighted wearable blankets on vital signs and infant movement in healthy infants during nap polysomnogram.
- Secondary Objective:**
 To investigate the efficacy of weighted wearable blankets on sleep patterns in healthy infants during overnight sleep.

Outcome Measures/Endpoints

Endpoints	Measurement	Timeframe
Heart Rate	EKG	At start, duration of nap
Respiratory Rate	Respiratory effort belts	At start, duration of nap
Body Temperature	Manual recording (Ear thermometer)	At start (before wrapping the participant in the blanket); at the end of the study and during a (feed) break (before unwrapping the participant from the blanket)
Oxygen Saturation	Pulse oximetry	At start, duration of nap
Infant Movement	Observation	Duration of nap

Eligibility

The target population for this study are healthy infants, aged 0-12 months, weighing at least 8 or more lbs. Individuals of any sex, race or ethnicity may participate. The study population is restricted to this specific age group because the objective is focused on the safety and efficacy of weighted wearable blankets on infants.

Inclusion Criteria

- Ability of parent, caregiver or legal guardian/representative to understand a written informed consent document and choose to participate in the study.
- 0-12 months of age
- Weight \geq 8 lbs
- Gestational age \geq 37 weeks
- Health status: healthy infant without underlying cardiac, neurological, or pulmonary disorders.
- Infant is naive to a weighted wearable blanket.

Exclusion Criteria

1. Health status: medical diagnosis associated with underlying cardiac, neurological, or pulmonary disorder.
2. Weight < 8 lbs
3. Gestational age < 37 weeks
4. Gestational use of marijuana, alcohol, or illicit drugs
5. Home environment: use of cigarettes, vaping, e-cigarettes, or marijuana

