- Informed consent – we will explain the study and ask for written consent; participants will receive a signed copy of the consent to keep
 - depending on how the participant was recruited, the informed consent discussion and written consent may have already occurred virtually
- Review of inclusion/exclusion criteria
- Collection of demographic data (infant age, sex, weight) and review of clinical data (current medications, other non-pharmacologic interventions, evidence of cardiac, neurological, or pulmonary disorders) from participant medical records and parent report
- Vital signs measurements (heart rate, respiratory rate, body temperature, oxygen saturation) will be obtained at baseline and monitored throughout the sleep study
- Height and weight measurements will be obtained once, at baseline
- Participants will be placed in weighted wearable blanket such that the blanket does not cover the head/face or restrain the infant
- Participants will then be put to sleep on their backs
- Vital signs will be monitored over a 6–8-hour period with standard polysomnography equipment
- Upon infant awakening at the end of the nap, the weighted wearable blanket will be removed, and vital sign measurements will be repeated
- One week after the nap polysomnogram, subjects will be contacted by phone to complete a short questionnaire

The following stopping parameters will be used for this study. Parameters are noted when the infant is quietly sleeping and the changes observed are not due to agitation or crying. Baseline data will be recorded before and after placing the infant into the weighted, wearable blanket.

Endpoint	Stopping Parameters
Heart rate	Persistent increase by >20 from baseline for 15 minutes
Respiratory rate	Persistent increase by >10 from baseline for 15 minutes
Body temperature	Increase by more than 2° from baseline
Oxygen saturation	Persistent drop by >10% from baseline
Infant movement	Agitation and unable to settle to sleep >15 minutes

If any of the stopping parameters are met, the weighted blanket will be opened to assess if the weighted blanket is responsible for the change. If determined yes, the weighted blanket will be removed and the nap polysomnogram will be terminated.

Reportable Events

We will follow the IU HRPP Reportable Events Policy and Guidance, as needed. Severe adverse events (SAEs) will be reported to the FDA in accordance with 21 CFR 312.32.

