The t-statistic and corresponding p-value will be calculated at a significance level of 0.05 alpha. If the p-value is less than 0.05, this will be interpreted as a statistically significant difference in the vital sign before and after wearing the weighted wearable blanket. If the p-value is greater than 0.05, this will be interpreted as no significant difference in the vital sign before and after wearing the weighted wearable blanket.

Reporting and Documentation of Results

Measures and Instruments

Polysomnography (PSG) Equipment

PSG will be conducted using a multi-channel PSG system Respiration Alice G3 that is designed for sleep studies. The system will include the following components: Electroencephalography (EEG) to measure brain activity, Electromyography (EMG) to monitor muscle activity, Electrooculography (EOG) to record eye movements, Electrocardiography (ECG) for heart rate monitoring, Respiratory effort belts to measure chest and abdominal movements, Nasal and oral airflow sensors to monitor airflow, Pulse oximetry to measure oxygen saturation levels, and Video recording for behavioral monitoring during sleep. Prior to each PSG recording, the equipment will be calibrated according to American Academy of Sleep Medicine (AASM) guidelines to ensure accurate measurements, and quality control checks will be performed regularly to ensure proper functioning of sensors and electrodes during the study. The following physiological variables will be continuously measured and recorded during PSG:

- Electroencephalography (EEG): EEG electrodes will be placed according to the international 10-20 system to record brain activity and identify sleep stages (e.g., wake, NREM, REM).
- Electromyography (EMG): EMG electrodes will be positioned to monitor muscle activity, including chin and limb muscles, to assess muscle tone and movements during sleep.
- Electrooculography (EOG): EOG electrodes will be used to detect eye movements, which are important for distinguishing sleep stages and identifying rapid eye movement (REM) sleep.
- Electrocardiography (ECG): ECG electrodes will be placed to monitor heart rate and detect any cardiac abnormalities during sleep.
- Respiratory Parameters: Respiratory effort belts will record chest and abdominal movements to assess breathing patterns; Nasal and oral airflow sensors will measure airflow and detect apnea and hypopnea events; and Pulse oximetry will monitor oxygen saturation levels.

Privacy/Confidentiality

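### The temperature stopping rule has no planned reading during sleep: temperature is said to be monitored throughout, but only ear readings outside sleep are scheduled

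*Combined protocol and SAP*

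**What the plan says.** All references are to the combined protocol and SAP.

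- **Stopping rule.** The stopping parameters table in Study Procedures gives, for body temperature, "Increase by more than 2° from baseline". The text above the table adds: "Parameters are noted when the infant is quietly sleeping and the changes observed are not due to agitation or crying".
- **Monitoring claim.** Study Procedures states: "Vital signs measurements (heart rate, respiratory rate, body temperature, oxygen saturation) will be obtained at baseline and monitored throughout the sleep study". It also states: "Vital signs will be monitored over a 6–8-hour period with standard polysomnography equipment".
- **Temperature schedule.** In Outcome Measures/Endpoints, heart rate, respiratory rate and oxygen saturation are measured at the start and for the whole nap. Body temperature is different. Its method is "Manual recording (Ear thermometer"), with one reading before wrapping and later readings "at the end of the study and during a (feed) break (before unwrapping the participant from the blanket").
- **Other time points.** Study Procedures asks for baseline data both before and after the infant is placed in the blanket. At the end of the session it says: "Upon infant awakening at the end of the nap, the weighted wearable blanket will be removed, and vital sign measurements will be repeated".
- **Equipment.** Measures and Instruments introduces its list with "The following physiological variables will be continuously measured and recorded during PSG". The list and the component list above it cover EEG, EMG, EOG, ECG, effort belts, airflow and oximetry; the components also include video. Neither contains a body temperature sensor.

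**The concern.** The paragraph before Objectives names overheating first among the risks to be assessed. It relies on a team member who watches vital signs continuously so that a problem can be corrected at once. Under Study Design the infant stays in the blanket until the polysomnogram is complete. Heart rate, respiratory rate and saturation each have a continuous channel to feed their stopping parameters. Temperature has only spot readings, none of them scheduled in sleep. An observer cannot see a 2° rise without measuring it, and nothing tells the observer when to measure.

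At stake is mainly the safety of the infants: a rise that develops between breaks could go unmeasured until the next break or the end. The temperature endpoint is also affected. It would describe breaks and the end of the session rather than sleep in the blanket, and its last value could be taken after the blanket is off.

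**Working it through.** The plan gives no figure to reproduce here. The check sets the planned readings side by side and then works out the gaps between them.

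**Step 1. Planned temperature readings**

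| Reading | Source | Blanket on? | During sleep? |
|---|---|---|---|
| Before wrapping | Outcome Measures/Endpoints; baseline data in Study Procedures | No | No |
| After wrapping (general baseline data) | Study Procedures | Yes | No, before sleep |
| Feed break | Outcome Measures/Endpoints | Yes | No; number and timing not stated |
| End, before unwrapping | Outcome Measures/Endpoints | Yes | No; the session is over |
| After removal (general repeat of vital signs) | Study Procedures | No | No |

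Scheduled readings during sleep: 0. The post-wrapping reading is itself a baseline, so it cannot show a rise from baseline. The end reading comes too late to shorten exposure. That leaves the break reading as the only planned value that could stop a session in progress.

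**Step 2. Longest gap between planned readings**

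Input: session length T = 6–8 h = 360–480 min (Study Procedures). Assumption: the start and end readings bound this period. With k breaks, the longest gap is at least T/(k + 1), and equals it only when the breaks are evenly spaced.

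- k = 1: 360/2 = 180 min; 480/2 = 240 min, so at least 3–4 h.
- k = 2: 360/3 = 120 min; 480/3 = 160 min, so at least 2–2.7 h.
- k = 0 (worst case): 360–480 min, so 6–8 h.

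The documents do not give k. These figures show a range and do not estimate what will happen.

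**Step 3. Interior readings needed for a one-hour longest gap**

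T/60 − 1: 360/60 − 1 = 5; 480/60 − 1 = 7. That is 5–7 per infant, or 50–70 across the minimum of 10 infants.

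**Step 4. Order at the end of the session**

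Outcome Measures/Endpoints takes the end temperature before unwrapping. Study Procedures removes the blanket and then repeats vital signs. Staff can do both: an ear reading first, then a repeat set after removal. But staff who work only from the Study Procedures list would record a value without the blanket, which is not a value during the intervention.

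**The case against.** The strongest defence is that the plan does name an instrument, and it places a team member with the infant who can use it at any time. Spot readings may be a deliberate trade-off, because an ear reading can wake the infant and disturb the other endpoints. On this view, rewording the monitoring sentence to match the endpoint table would settle the matter. Part of this stands: a method exists, and what is missing is an interval or an instruction to use it during sleep. But rewording alone would remove the textual conflict and leave the rule without data between breaks.

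A reader might infer four stronger things that the documents do not support.

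- *The rule can never trigger.* A break reading, or an unscheduled one, could trigger it. The quiet-sleep sentence is aimed at changes caused by agitation or crying, and nothing bars acting on a calm break reading. The plan simply does not say that it counts.
- *The two end-of-session instructions contradict each other, so infants would have no with-blanket temperature after baseline.* Both can be followed. That outcome needs the general instruction to replace the specific one, and also no break.
- *Infants will go 6–8 h without a reading.* The feed break is one of the listed time points, so this is the extreme case.
- *The paired comparison is invalid.* A paired t-test needs only one on-blanket value per infant, and the break and pre-unwrapping readings can supply it.

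**Conclusion.** The concern holds as a gap in safety monitoring. The plan says temperature is monitored throughout and attaches a stopping rule to it, yet it schedules no reading in sleep and lists no sensor that would provide one. Between breaks the rule depends on an unscheduled reading that no instruction requires.

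The size depends on breaks, which the plan does not specify. The longest unmeasured gap is at least 3–4 h with one break and 6–8 h at worst, assuming that the start and end readings bound the 6–8 h session. The end-of-session order is a lesser point: it is unclear rather than contradictory. The presence of staff lessens the risk but does not close the gap. The change should be made, and it needs no change to the design or sample size.

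**What to change.** Amend the protocol in three places.

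1. **Interval.** In Outcome Measures/Endpoints and Study Procedures, have the team member already present take temperature with the blanket on at a fixed interval during the session, including sleep. Hourly readings with the existing ear thermometer are one example; the interval is a clinical choice.
2. **Trigger.** State beside the stopping parameters table that a reading from a calm, awake infant at a break can trigger the temperature rule.
3. **End reading.** Amend Study Procedures so that the end temperature is taken before the blanket is removed, with any post-removal reading additional.

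Cost: one amendment, no extra infants, and about 5–7 added readings per infant if hourly (50–70 for 10 infants). Some readings may disturb sleep, so their times should be recorded. A continuous skin or axillary probe would avoid repeated handling, but it is an alternative only if a baseline and threshold are set for that site. The documents do not say whether the recorder accepts a temperature input, so a separate device might be needed.

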6. Infant is not naive to a weighted wearable blanket.

Study Design

Direct observational pilot study of the safety of weighted wearable blankets on a minimum of (10) healthy infants aged 0-12 months with nap polysomnogram. Participants will be placed in a weighted wearable blanket, in accordance with their age/weight/height, by their parent or caregiver under the supervision of a member of the study team. After being put to sleep on their back, the participant will remain in the weighted wearable blanket until completion of the nap polysomnogram.

Enrollment/Recruitment

The target number of total participants is a minimum of 10 infants. The recruitment strategy aims to achieve representation of minority groups that reflects the demographics of the population in the catchment area. At least 5 infants must be 0-3 months and all others can be any age between 0 and 12 months of age.

Participants will be recruited in a variety of ways:

Flyers will be posted in the hospital(s) and/or on campus in places frequented by potential participants (e.g., elevators, food courts, parking garage elevators) or public places such as parks, grocery stores or churches. In addition, we will provide flyers and/or brochures to the various maternity wards at Riley, University & Methodist.

Brochures will be available for patients referred to the Sleep Center at Riley or established patients at a clinic visit. Patients who are already scheduled for a sleep study, and meet eligibility criteria, will be contacted by phone and introduced to the study. If the patient is interested, we will send the brochure and the consent (either by USPS or email).

The flyers and brochures will be shared with faculty physicians (in the division of Pediatric Pulmonology, Allergy and Sleep Medicine) as well as RN and other staff in the Sleep Center and maternity wards (for informational purposes only, they will not consent subjects). We might also include the flyer in weekly newsletters and/or internal communications.

Social media ads will be placed on Facebook and/or Instagram and clicking on this ad will direct potential participants to the study's web site

(<https://dreamlandbabyco.com/pages/clinical-trial>) where they can find phone and email information for the study team.

Study Procedures

During this study, participants will have one study visit. This visit will take place in the Sleep Center at Riley Hospital for Children at IU Health.

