An adverse event (AE) is defined as any untoward medical occurrence associated with the use of a drug or device in humans, whether or not considered drug- or device-related. An SAE is defined as an adverse event or suspected adverse reaction is considered "serious" if, in the view of the investigator, it results in any of the following outcomes: Death, a life-threatening adverse event, inpatient hospitalization or prolongation of existing hospitalization, a persistent or significant incapacity or substantial disruption of the ability to conduct normal life functions, or a congenital anomaly/birth defect. Important medical events that may not result in death, be life-threatening, or require hospitalization may be considered serious when, based upon appropriate medical judgment, they may jeopardize the patient or participant and may require medical or surgical intervention to prevent one of the outcomes listed in this definition. Collection of AEs and SAEs will begin at the time of consent.

Loss of confidentiality is always a potential adverse event and will be reported per existing Indiana University and Indiana University Health policies.

Study Withdrawal/Discontinuation

Participants are free to withdraw from participation in the study at any time for any reason.

The study team may discontinue a participant from the study for any of the following reasons:

- Unacceptable adverse event(s)
- Significant study intervention non-compliance
- The participant meets an exclusion criterion (either newly developed or not previously recognized) that precludes further study participation

Statistical Considerations

Sample Size Considerations

In the pilot safety study, the total sample size will be a minimum of 10 infants. All participants will receive the same intervention. Data from all participants who complete both baseline and follow-up assessments will be included in the analysis.

Statistical Analysis Plans:

Primary Analysis (Safety)

Means and standard deviations for each vital sign will be calculated at both baseline and during the intervention. Summary statistics based on demographic and baseline characteristics will be gathered. A Paired t-test will be performed to compare the means

of each vital sign at baseline and during the intervention. We will also use a linear mixed effect model to determine differences in vital signs.

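### The late-exclusion clause has no cut-off at blanket placement, so with the completers-only analysis set an infant discontinued for an abnormality first seen in the blanket can be lost from the primary vital-sign analysis

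*Combined protocol and SAP*

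**What the plan says.** All references are to the combined protocol and SAP.

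- **Study Withdrawal/Discontinuation.** The decision is discretionary: "The study team may discontinue a participant from the study for any of the following reasons". The third listed reason is "The participant meets an exclusion criterion (either newly developed or not previously recognized) that precludes further study participation". Nothing limits it to the period before the blanket goes on.
- **Exclusion Criteria, item 1.** "Health status: medical diagnosis associated with underlying cardiac, neurological, or pulmonary disorder".
- **Study Procedures.** Eligibility is reviewed before placement. The clinical review covers "evidence of cardiac, neurological, or pulmonary disorders) from participant medical records and parent report".
- **Study Design.** After being put to sleep, "the participant will remain in the weighted wearable blanket until completion of the nap polysomnogram". The procedures place the infant in the blanket first and put the infant to sleep afterwards. No sleep recording without the blanket is described.
- **Polysomnography (PSG) Equipment.** "Nasal and oral airflow sensors will measure airflow and detect apnea and hypopnea events", and "ECG electrodes will be placed to monitor heart rate and detect any cardiac abnormalities during sleep".
- **Sample Size Considerations.** "Data from all participants who complete both baseline and follow-up assessments will be included in the analysis". Follow-up assessments are not defined, no set of all exposed infants is named, and nothing says whether a discontinued infant's data are kept.
- **Primary Analysis (Safety).** Means and standard deviations, a paired t-test for each vital sign, and a linear mixed model.

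**The concern.** In a one-visit study, the main new information about an infant's heart, lungs or nervous system after the eligibility review is the polysomnogram, which is recorded in the blanket. If a disorder that nobody had recognised comes to light during the session, it may well do so through the same recording that supplies the safety data. Without an unwrapped sleep recording, the study cannot readily separate a prior disorder from an effect of the blanket.

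The clause allows discontinuation on that evidence, and the completers-only sentence can then take the infant out of the analysis. Membership of the primary safety set would depend partly on what happened under exposure. Recruitment makes this more than theoretical, because infants already scheduled for a sleep study may be approached, and unrecognised disorders are more plausible among them than among community volunteers.

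**Working it through.** The plan gives a minimum of 10 infants with no power, effect size or standard deviation, so there is no stated calculation to reproduce. The check has two parts.

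**1. When does a discontinued infant leave the analysis?** This depends on how follow-up assessments is read.

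| Reading of follow-up | Discontinued during the nap | Discontinued after the nap, before the one-week call |
|---|---|---|
| Vital signs during the intervention | Unclear: partial recording | Kept |
| Repeat vital signs at the end of the nap | Out, unless they were still taken | Kept |
| One-week telephone questionnaire | Out, unless the call is still made | Out, unless the call is still made |

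The analysis-set sentence is not confined to the t-test. A mixed model could use a partial record, but the plan as written does not say that it will.

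**2. What can one loss do to the result?** Assumed values, for illustration only: nine infants with a mean change of -0.5 saturation points, and one with -8.

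- All ten: (9 × -0.5 + 1 × -8) / 10 = -12.5 / 10 = **-1.25**.
- Without that infant: **-0.5**. The ratio is 1.25 / 0.5 = 2.5.

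If the 10% saturation limit among the stopping parameters is read in percentage points, a fall of 8 does not reach it. The illustration therefore does not depend on a protocol stop.

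The p-value also needs the SD of change among the nine, s, which the plan does not give. With all ten, the sum of squares about the mean is 8s² + 9 × 0.75² + 6.75² = 8s² + 50.625, and t = -1.25 / √(SS / 9 / 10) on 9 df. With nine, t = -0.5 / (s / 3) on 8 df. P-values are two-sided, which is an assumption because the plan does not state sidedness.

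| Assumed s | SS, all ten | All ten: t, p | Infant removed: t, p |
|---|---|---|---|
| 0.5 | 52.625 | -1.63, 0.14 | -3.00, 0.017 |
| 1.0 | 58.625 | -1.55, 0.16 | -1.50, 0.17 |

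At s = 0.5 removal turns a non-significant fall into a significant one, because the outlying infant inflates the SD more than it moves the mean. The switch occurs for s below 1.5 / 2.306 = 0.65. At s = 1.0 removal raises the p-value slightly and neither result is significant.

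**How often could it arise?** The chance that at least one of 10 infants is affected is 1 - (1 - p)^10. Over assumed true risks of 2%, 5%, 10% and 20% this is 18%, 40%, 65% and 89%. This is the chance that the situation exists, not the chance that the clause is used.

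**The case against.** The strongest reply is that this is a routine clause about further participation, not about data. It says discontinue; it does not say reclassify, replace or delete. That stands, and it rules out several stronger readings that a reader might infer.

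- *That the event would go uncounted as a safety outcome.* The documents do not support this. Adverse events are collected from consent whether or not they are thought device-related, and an unacceptable adverse event is a separate ground for discontinuation. However, the primary analysis section plans no adverse event summary, so the record does not replace the lost vital-sign data.
- *That the polysomnogram serves as an eligibility test.* It is never named as one. Eligibility rests on records and parent report before placement, and exclusion 1 requires a diagnosis, not an isolated event on a trace. The text neither provides for this use nor forbids it.
- *That an infant with complete data can be removed anyway.* On its face the completers sentence keeps such an infant. The problem is therefore not separate from the completers rule; it arises from the two provisions together and from the undefined follow-up.
- *That the selection always favours a finding of safety.* In the illustration the mean fall does shrink, but the table shows that the significance test can move in either direction.
- *That an event rate would fall from 1/10 to 0/9.* The arithmetic is right, but no event-rate analysis is planned, and apnea and ECG abnormality are not listed endpoints.

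What remains is the missing cut-off and the missing all-exposed set. There is also a sign that the clause was not drafted with exposed infants in mind: exclusion 6 bars infants who are not naive to the blanket. Read literally with the words on newly developed criteria, every infant meets it once wrapped.

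**Conclusion.** The point holds as a gap left by silence, not as a rule that requires removal. An infant discontinued because of an abnormality first seen in the blanket can be lost from the paired t-test and mixed model when the plan is followed as written. Whether that happens depends on an undefined term that could be settled after the data are seen.

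At the minimum sample size, one such infant is 10% of the data. In the illustration the estimated mean fall drops from 1.25 to 0.5 saturation points, with an unpredictable effect on the p-value. Those sizes rest wholly on assumed changes and SDs, since the documents give none. That the route exists rests on the text alone. It should be closed before analysis, and preferably before enrolment.

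**What to change.** Four changes, all to the analysis provisions:

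1. State that eligibility for analysis is judged only on information that existed before blanket placement and is independent of the study recording, such as gestational age, prior blanket use or a diagnosis already in the medical record.
2. Define the primary safety set as all infants placed in the blanket, using their data up to discontinuation, in place of the completers sentence.
3. Report every post-placement discontinuation with its reason and timing.
4. Add a sensitivity summary without infants later confirmed to have a pre-existing disorder.

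This costs one amended bullet and a few sentences in the analysis section. The drawback is that an infant with a truly pre-existing disorder may remain in the main summary; the sensitivity summary shows how much that matters. Clinical stopping of a session is unaffected.

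### The analysed data depend on an undefined follow-up assessment, and no summary of stopping events, terminations or adverse events is planned

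*Combined protocol and SAP*

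**What the plan says.** **Analysed data.** Sample Size Considerations gives the only statement: "Data from all participants who complete both baseline and follow-up assessments will be included in the analysis".

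**What follow-up could be.** Three events fit the word:
- The recording in the blanket. Primary Analysis (Safety) says "Means and standard deviations for each vital sign will be calculated at both baseline and during the intervention", and the paired t-test compares the same two periods.
- The closing measurement. Study Procedures says "Upon infant awakening at the end of the nap, the weighted wearable blanket will be removed, and vital sign measurements will be repeated". The rule for reading a p-value below 0.05 leans this way: "this will be interpreted as a statistically significant difference in the vital sign before and after wearing the weighted wearable blanket".
- The telephone call. Study Procedures says "One week after the nap polysomnogram, subjects will be contacted by phone to complete a short questionnaire".

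**Early endings.** If a stopping parameter is met and the blanket is judged responsible, "the weighted blanket will be removed and the nap polysomnogram will be terminated" (Study Procedures). Study Withdrawal/Discontinuation also lets the team discontinue an infant for an unacceptable adverse event. Neither section says how that infant's data are analysed.

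**Events.** Under Reportable Events, adverse events are collected from consent and serious ones go to the FDA. The Statistical Analysis Plans contain means and SDs, demographic and baseline summaries, paired t-tests and a linear mixed model. No summary of stopping events, terminations or adverse events is listed there, and the heading Reporting and Documentation of Results adds none.

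**Temperature.** The endpoint table plans ear-thermometer readings at the start and "at the end of the study and during a (feed) break (before unwrapping the participant from the blanket". Study Procedures says "Vital signs measurements (heart rate, respiratory rate, body temperature, oxygen saturation) will be obtained at baseline and monitored throughout the sleep study".

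**The concern.** This is a pilot whose primary purpose is safety. An infant whose nap is ended because of the blanket is among the most informative observations it can produce, and the plan leaves two things open for that infant.

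The first is membership of the analysis. If completing follow-up requires something a stopped infant may not have, inclusion depends on the outcome being studied. With about 10 infants, losing one or two can change the estimate.

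The second is visibility. Even an infant who stays in contributes only to a mean. Means and p-values do not show how many infants met a stopping parameter, so the planned results could be reported in full without that number.

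**Working it through.** There is no plan figure to reproduce: the minimum of 10 infants has no derivation, and the documents give no mean change, SD or stopping rate. The text settles steps 1, 2 and 6. Steps 3 and 4 use assumed inputs, labelled as such. Step 5 is exact.

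**1. Which readings can exclude a stopped infant**
- *On-blanket recording:* heart rate, respiratory rate and saturation exist up to removal, so the infant stays in.
- *Vital signs on awakening:* the infant drops out only if these are not taken after a stop. The documents do not say either way.
- *Telephone call:* the infant drops out only if the call is missed. This reading is weak, because the planned analyses concern vital signs and nothing says the call collects them.

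**2. Direction, if exclusion occurs.** The rules for heart rate, respiratory rate and temperature act on increases, so excluding stopped infants pulls the mean change down. The saturation rule acts on a drop, so exclusion pulls that mean change up. A true fall in heart or respiratory rate would be exaggerated, not hidden. Signs that did not trigger the stop move only through their correlation with the one that did.

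**3. Size for one stopped infant in 10 (assumed).** Let nine infants have a mean heart-rate change of +2. Let the tenth show no change for *m* minutes, then +25 for 15 minutes (the rule is more than 20 above baseline for 15 minutes), then be stopped.
- Stopped infant's on-blanket mean = (15 × 25) / (m + 15)
- All-infant mean = (9 × 2 + that value) / 10

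| m | Stopped infant's mean | All 10 | Nine completers |
|---|---|---|---|
| 0 | 375/15 = 25.0 | 43.0/10 = 4.3 | 2.0 |
| 30 | 375/45 = 8.3 | 26.3/10 = 2.6 | 2.0 |
| 240 | 375/255 = 1.5 | 19.5/10 = 1.9 | 2.0 |

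Exclusion therefore moves the estimate by anything from almost nothing to 2.3 bpm. The last row also shows that an infant who is kept in but stopped late is invisible in the mean.

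Simulations with n = 10 give the same spread. Assumptions: the stop comes at the first 15-minute block mean above +20, in 24 blocks; lag-1 correlation 0.5; within-infant SD 3 or 5; half or all stops attributed to the blanket and excluded. A true mean of +2 (SD 5) gives completer means of 1.4 to 1.9. A true mean of +10 (SD 10) gives 2.6 to 7.9. Under a stricter rule, with every minute above +20 for 15 minutes, the ranges are 1.9 to 2.0 and 5.1 to 8.3. Neither model includes the protocol's quiet-sleep condition, which would reduce stops.

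**4. Chance that the question arises.** P(at least one stop in 10) = 1 − (1 − p)^10. For assumed p of 1%, 5%, 10% and 20% this is 10%, 40%, 65% and 89%.

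**5. What a count would report.** Exact (Clopper-Pearson) 95% intervals:
- 0/10: 0 to 30.8% (upper limit 1 − 0.025^(1/10) = 0.308)
- 1/10: 0.3 to 44.5%
- 2/10: 2.5 to 55.6%

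**6. Temperature.** The endpoint table describes intermittent manual readings, and Study Procedures lists temperature among the signs monitored throughout. The continuously recorded polysomnography variables under Measures and Instruments do not include it. An infant stopped on temperature must have an on-blanket reading, since that reading triggered the stop. For an infant stopped on another sign before any feed break, the text does not settle whether one exists.

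**The case against.** The completer sentence says who will be included. It does not say only, and it excludes no one by name. Primary Analysis (Safety) twice states its comparison as baseline against the intervention period, which makes the on-blanket recording the natural second assessment. A mixed model can use partial recordings. Adverse events are collected and serious ones reported, so nothing is lost to oversight. The size of any bias rests wholly on assumed inputs.

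Most of this stands, and it rules out several stronger statements that a reader might infer:
- *That the plan excludes stopped infants.* It does not say so. Exclusion needs the awakening reading and also skipped closing measurements.
- *That a stopped infant goes unreported.* Collection and regulatory reporting are in place. What is missing is a planned summary in the results.
- *That the analysis would show 0 of 9 stopped instead of 1 of 10.* No stopping proportion is planned, so neither figure would appear.
- *That temperature is in doubt for every stopped infant.* Step 6 limits this to stops on another sign.

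What does not stand is that the natural reading closes the matter. The p-value rule speaks of before and after wearing, the completer sentence does not exempt the mixed model, and no other analysis set is given. Most stopping events would probably not be serious adverse events, so regulatory reporting does not replace a count.

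**Conclusion.** The point holds as two gaps of different strength.

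The firm one needs no assumption: on any reading, the planned results of this safety pilot contain no summary of stopping events, blanket-attributed terminations or adverse events.

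The conditional one is outcome-dependent exclusion. Follow-up is undefined and terminated or discontinued infants have no analysis rule, so exclusion is possible but not stated, and the more natural reading avoids it for heart rate, respiratory rate and saturation. If it occurs, the bias runs against the direction of the triggering sign's stopping rule. The illustrations run from negligible to large, and their large end needs either an early stop or a sizeable average effect. The one pilot in the background that reports no significant change in temperature or breathing rate fits the small end, though in infants with Neonatal Abstinence Syndrome.

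Both gaps should be closed before the data are analysed.

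**What to change.** - Replace the completer sentence with a safety analysis set of every infant placed in the blanket.
- Define the post-baseline value as all on-blanket data up to removal, including the readings that triggered a stop, in both the paired comparison and the mixed model.
- Report the number and proportion of infants meeting each stopping parameter and any stopping parameter, and the number attributed to the blanket and terminated, with exact 95% intervals as in step 5. Add an adverse event summary.
- Keep the completer analysis as a sensitivity analysis, with follow-up defined.
- Reconcile the endpoint table with Study Procedures on when temperature is read. Report temperature as missing, with the reason, where no on-blanket reading exists.

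**Cost.** Wording and slightly more analysis, with no extra infants or visits; heart rate, respiratory rate and saturation are already recorded continuously. The drawback is that stopped infants contribute shorter recordings ending on an extreme reading, which shifts the all-infant mean slightly in the direction of the stopping rule. In the block-mean simulation it came to 10.1 to 10.5 for a true +10, and 2.0 to 2.1 for a true +2.
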